6.3.2 COVARIATE ADJUSTMENT

Not applicable.

6.3.3 ASSUMPTION CHECKING

The Shapiro Wilks test will be performed to evaluate the normality.

6.3.4 ALTERNATIVE METHODS IF DISTRIBUTIONAL ASSUMPTIONS NOT MET

Without the normality assumption, we will consider a non-parametric tests: Friedman test and Wilcoxon or Sign test. Since the primary outcome is a count variable it may be more suited to methods that utilize the Poisson distribution. If the primary outcome conforms to a Poisson distribution rather than a normal distribution then Poisson regression will be considered. Effect estimates and 95% confidence intervals will be tabulated.

6.3.5 SENSITIVITY ANALYSES

Not applicable.

6.3.6 SUBGROUP ANALYSES

Not applicable.

Short title:	BRAINTRAIN SAP Template

6.4 MISSING DATA

Mean imputation, this is, the replacement of a missing observation with the mean of the non-missing observations for that variable.

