8.1 Number of participants

A total of 15 (plus 3 in case of drop outs) participants will be recruited. We expect to recruit one subject each three weeks. The study is expected to start on the second semester of 2015 and last up to 82 weeks (including follow-up).

8.2 **Recruitment process**

Participants will be recruited from the National Clinical Program for ASD at University of Coimbra. The Lead Researcher is responsible for contacting the participants.

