13.3 Missing, unused & spurious data

Detail provided in the Statistical Analysis Plan (SAP).

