15.1 Main analysis

A priori, we will analyse the data normality. Considering a normal distribution of the mean differences, the main analysis will consist on a t-test on the means - difference between two dependent means (matched pairs).

The null hypothesis of this test is that the means μ_x , μ_y of pre- and post- intervention, respectively, are identical.

The null hypothesis that $\mu_x = \mu_y$ can be reformulated in terms of the difference $d_i = x_i - y_i$. The null hypothesis is then given by $\mu_d = 0$. The alternative hypothesis states that μ_d has a value different from zero:

 $H_0: \mu_d = 0$

 $\mathsf{H}_{\mathtt{l}}:\mu_{\mathtt{d}} \neq 0$

However, without the normality assumption, we will consider a non-parametric Wilcoxon test.

Further details will be found in the SAP

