3.3 SAMPLE SIZE

To determine de sample size, we used the G*Power tool (Faul, Erdfelder, Lang & Buchner, 2007):

Test family: t-test;

Statistical test: Means (difference between two different means);

Type of power analysis: A priori; Fixed input parameters: Tail(s): Two;

α err prob: 0.05;

Output: Estimated sample size

		Effe	ect Siz	e dz (ES)
		0.8	0.9	1.0	1.1
	0.7	12	10	9	8
Power	0.8	15	12	10	9
	0.9	19	16	13	11

with
$$ES = Cohen's \ dz = \frac{M_{diff}}{\sqrt{\frac{\sum (x_{diff} - M_{diff})^2}{N-1}}}$$
. Based in other effects described in the literature, the effect

size considered is 0.8 (the means difference is 0.8 standard deviations). In these conditions, for power of 0.8 the estimated sample size is 15.

Without the normality assumption of the distribution of the means differences, we would also need 15 subjects, considering a non-parametric test.

Assuming a 20% dropout rate (based on literature) the sample size will be 18.

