4.3 ANALYSIS POPULATION

The intention-to-treat population will include all participants irrespective of number of session completed. If required the Centre for Trials Research will investigate methods of analysis that adjust for the number of sessions completed which is preferable to excluding participants which may result in biased results.

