6.3 ANALYSIS METHODS

6.3.1 LIST OF METHODS AND PRESENTATION

Initially will conduct an exploratory data analysis using graphical techniques (box and scatter plots) and quantitative analysis (statistical measures and frequency table) in order to characterize the sample, detect possible extreme outliers and measurement error.

To detect differences between the three time points of neuropsychological evaluation (session 1, session 7 and follow-up) will perform the Repeated-measures ANOVA. To identify the difference between each evaluation, 95% confidence intervals will be presented. (Note: considering a normal distribution)

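### Filling missing visit scores with the visit mean (SAP 6.4) gives primary-outcome p-values and 95% intervals that miss their stated error rates, even under completely random loss

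*SAP*

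**What the plan says.** SAP 6.4 is one sentence: "Mean imputation, this is, the replacement of a missing observation with the mean of the non-missing observations for that variable". It does not say whether a variable is the total score at a visit or a single questionnaire item, and it makes no exception for the primary outcome. Protocol 13.3 refers the whole topic to the SAP. SAP 6.3.5 marks sensitivity analyses as not applicable.

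The rule feeds two candidate main analyses. Protocol 15.1 plans a paired t-test of pre against post. SAP 6.3.1 plans a three-visit comparison: "To detect differences between the three time points of neuropsychological evaluation (session 1, session 7 and follow-up) will perform the Repeated-measures ANOVA". SAP 4.1 promises two-sided 95% intervals.

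Missing scores are expected. SAP 3.3 states: "Assuming a 20% dropout rate (based on literature) the sample size will be 18". SAP 4.3 keeps people in the analysis: "The intention-to-treat population will include all participants irrespective of number of session completed". That section also mentions possible adjustment for sessions completed, but this concerns attendance and not absent scores.

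**The concern.** A participant with a baseline but no session-7 or follow-up score receives the average of those who have one. The paired test or ANOVA then treats the full sample as measured. The filled value adds to the sample size without adding information, sits exactly at the visit mean, and has no link to that person's own baseline. The reported standard error is therefore wrong even under the mildest assumption, that scores are missing completely at random.

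The trial has one arm, so the pre-post change is the whole result and there is no control group in which the error could cancel. If people leave for reasons related to their scores, bias in the estimated change comes on top. Low scorers leaving pushes the estimated improvement up, and high scorers leaving pushes it down. The documents do not say which to expect.

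**Working it through.** **1. The plan's own figure.** Inputs from Protocol 13.2 and SAP 3.3: two-sided alpha 0.05, power 0.80, dz = 8/10 = 0.8. Exact noncentral-t power for a paired test is 0.790 at n = 14 and 0.821 at n = 15, so 15 is confirmed. All 12 cells of the SAP table also match. The 18 enrolled is 15 × 1.2, which allows 3 losses; 20% of 18 is 3.6, or 4 rounded up.

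**2. Algebra, completely random loss.** Let s be the SD at one visit, ρ the pre-post correlation (not in the documents; 0.3-0.8 assumed), n = 18, and m the number of observed post scores. An SD of the difference of 10 means s² = 100/[2(1−ρ)].

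- True variance of the mean change after filling: s²[1/m + (1−2ρ)/n]
- Variance the paired t-test uses, on average: (s²/n)[1 + (1−2ρ)(m−1)/(n−1)]

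With 3 missing (m = 15):

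| ρ | s² | true variance | variance used | ratio | SE ratio |
|---|---|---|---|---|---|
| 0.3 | 71.4 | 6.35 | 5.28 | 0.83 | 0.91 |
| 0.5 | 100 | 6.67 | 5.56 | 0.83 | 0.91 |
| 0.8 | 250 | 8.33 | 7.03 | 0.84 | 0.92 |

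The ratio is close to m/n = 15/18 = 0.83 throughout. The 15 observed pairs alone have variance 100/15 = 6.67 at any ρ, so at ρ = 0.8 filling is less precise than leaving the gaps and also understates its error.

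**3. Type I error by simulation.** Settings: normal scores, equal correlations, no true change, the same people missing at both later visits, 100,000 trials per setting, ρ 0.3-0.8.

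| Missing of 18 | Paired t-test | Three-visit ANOVA | Reported/true SE |
|---|---|---|---|
| 1 | 5.5-5.6% | 6.1% | not tabulated |
| 2 | 5.9-6.3% | 7.3-7.6% | not tabulated |
| 3 | 6.5-7.0% | 8.7-9.3% | 0.90-0.92 |
| 4 | 7.3-8.1% | 10.5-11.5% | 0.87-0.89 |

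Observed pairs give 4.9-5.1%. A separate run over ρ 0-0.9 gave 5.8-7.3% and 8.1-9.5% with 3 missing, and paired-interval coverage of 92.7-94.2%. The SAP 6.3.4 fallback tests do not escape: with 3 missing and ρ 0.3-0.9, Wilcoxon is at 6.1-7.0% and Friedman at 10.4-11.3%.

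**4. Bias, as illustration.** If 3 drop-outs sit 10 points below completers and would have stayed there, filling adds 3/18 × 10 = 1.7 points of false improvement, or 1.67/8 = 21% of the 8-point target. With 4 it adds 2.2 points. If 3 sit 10 points above, it subtracts 1.7. If instead the 3 lowest baselines leave, the bias is +0.7, +1.4 and +3.6 points at ρ = 0.3, 0.5 and 0.8. Reported/true SE is then 0.95, 1.01 and 1.22, so the SE is not always too small.

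**5. The replacement.** A three-visit unstructured REML model was simulated with about 1,600-2,150 trials per setting (Monte Carlo SE about 0.5 percentage points). Type I error of the session-7 contrast:

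| Missing | Satterthwaite df | Normal limits |
|---|---|---|
| 3 | 4.4-5.0% | 6.0-7.1% |
| 4 | 5.8-6.0% | 7.5-8.4% |

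When the 3 lowest baselines leave, the mixed model has bias 0.0 and observed pairs −1.7 to −0.9. When 3 drop-outs sit 10 points low throughout, observed pairs have bias 0.0 and the mixed model keeps 1.67 × (1−ρ) = 1.2, 0.8 or 0.3 points. Neither analysis covers both cases.

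**The case against.** The effect is conditional, and several limits stand.

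- **Number filled.** Someone who stops sessions may still give a post score, and someone who withdraws their data leaves nothing to fill. With no missing scores the rule does nothing.
- **Pattern.** The main figures assume loss at both later visits. If only the 6-month follow-up is missed, the baseline-to-session-7 paired test stays at 5.0-5.2%. The ANOVA still moves to 6.6-7.0% with 3 missing.
- **Reading.** If the mean were pooled over all visits, pre-post type I error would stay near 5% (4.7-5.1%), but a real change would be pulled toward zero. If only questionnaire items were meant, the SAP has no rule for missing visits. No reading yields a sound analysis of visit scores.
- **Which test.** SAP 6.3.1 ties the ANOVA to neuropsychological evaluation, which SAP 3.6 lists apart from the joint-attention task. SAP 6.3.4 discusses the primary outcome under the same methods. The text is ambiguous, so both tests are reported here.
- **Feasibility.** Protocol 6 describes basic science and clinical feasibility, but it also classifies the trial as an efficacy study, and SAP 3.4 says the main outcomes test superiority.
- **Remedy.** Under completely random loss observed pairs already hold 5%, and the mixed model is slightly above it with 4 missing. Making it primary rests on accepting that missingness depends on observed scores. That is why the paired analysis is kept beside it.

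**Conclusion.** The concern holds, and the rule must be changed before analysis. Under the visit-mean reading, at the planned loss of 3 to 4 of 18 at both later visits, a nominal 5% test runs at 6.5-8.1% (paired t-test) or 8.7-11.5% (ANOVA), and the reported SE is 0.87-0.92 of the true one. This rests on normal scores, completely random loss and an assumed correlation of 0.3-0.8; the direction was the same for every correlation tried from 0 to 0.9. The inflation is modest on the protocol's paired test and larger on the SAP's ANOVA. Bias from non-random loss is additional, of unknown sign, and its size here is illustrative only. The sample size of 15 is not in dispute.

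**What to change.** Delete mean imputation. Replace SAP 6.4 with:

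> Missing visit scores are not imputed. All observed scores are analysed with a REML mixed model for repeated measures: visit as fixed effect, unstructured within-participant covariance, Satterthwaite degrees of freedom. The model assumes that missingness depends only on observed scores.

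Replace SAP 6.3.5 with:

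> Sensitivity analysis: paired baseline-to-session-7 analysis of participants with both scores. Neither analysis removes all bias under other missingness mechanisms. Numbers observed at each visit, and reasons for missing scores, are reported.

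Amend SAP 6.3.1 to name this model for the primary outcome, and align Protocol 15.1, which still calls the paired t-test the main analysis. The no-imputation rule also governs the fallback tests in SAP 6.3.4; say that they use participants with the scores each test needs. If 6.4 was meant only for single questionnaire items, say so.

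**Cost.** Wording and a little more analysis work, with no new data. Protocol 13.4 may require a substantial amendment. With 3 missing, the mean 95% half-width for the session-7 change becomes 5.2-5.3 points against 4.8-4.9 under mean filling at correlation 0.3-0.5 (8-10% wider), and 5.3 against 5.5 at 0.8. Small-sample type I error is close to 5%, not exact.

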6.5 ADDITIONAL ANALYSES

Not applicable.

6.6 HARMS

The number (and percentage) of patients experiencing each AE/SAE will be presented categorised by severity. For each patient, only the maximum severity experienced of each type of AE will be displayed. The number (and percentage) of occurrences of each AE/SAE will also be presented. No formal statistical testing will be undertaken.

6.7 STATISTICAL SOFTWARE

The analysis will be carried out using SPSS 23.0.

7. REFERENCES

7.1 NON STANDARD STATISTICAL METHODS

Not applicable.

7.2 DATA MANAGEMENT PLAN

This documents follows the instructions stated in the Data Management Plan (DMP) version 1.0.

- 7.3 TRIAL MASTER FILE AND STATISTICAL MASTER FILE
- 7.4 OTHER SOPS OR GUIDANCE DOCUMENTS

SAP DEVIATION LOG

Document number:		Document version:	
Reason for deviation:
